4.2.1 Abemaciclib Dose Modification and Management

Please refer to the following tables for dose modifications for adverse reactions related to abemaciclib. If dose reduction is necessary, decrease the dose by 50 mg at a time. Discontinue abemaciclib for patients unable to tolerate 50 mg twice a day (BID).

Abemaciclib Dose Modifications for Adverse Events

Dose Level	Abemaciclib dose in combination with fulvestrant
Recommended Starting Dose	150 mg
First Dose Reduction	100 mg
Second Dose Reduction	50 mg
Third Dose Reduction	Not applicable

Hematologic Toxicities

Hematologic toxicities including neutropenia, leukopenia, anemia, and thrombocytopenia have been observed in patients treated with abemaciclib, and causality has been established. Severe (Grade 3 and 4) neutropenia was observed in patients receiving abemaciclib. Patients should be monitored closely for signs of infection, anemia, and bleeding.

Hematologic Toxicity Dose Management Guidelines
Monitor complete blood counts prior to the start of abemaciclib therapy, every 2

CONFIDENTIAL

This material is the property of the [UC Irvine Chao Family Comprehensive Cancer Center](#). Do not disclose or use except as authorized in writing by the study sponsor.

weeks for the first 2 months, monthly for the next 2 months, and as clinically indicated.

CTCAE Grade	Action
Grade 1-2	No dose modification required
Grade 3	Suspend dose until toxicity resolves to \leq Grade 2. Dose reduction is not required.
Grade 3, recurrent, or Grade 4	Suspend dose until toxicity resolves to \leq Grade 2. Resume at next lower dose.

If blood cell growth factors are required, suspend abemaciclib dose for at least 48 hours after the last dose of blood cell growth factor and until toxicity resolves to \leq Grade 2. Resume at next lower dose unless already performed for the toxicity that led to the use of the growth factor. Growth factor use as per current treatment guidelines.

Hepatic Toxicities

Alanine aminotransferase (ALT) and aspartate aminotransferase (AST) elevation are considered as ADR with the use of abemaciclib. The following information in Table 3 must be included in investigator-sponsored protocols for hepatic monitoring:

Hepatic Toxicity Dose Management Guidelines	
Monitor ALT prior to the start of abemaciclib therapy, every 2 weeks for the first 2 months, monthly for the next 2 months, and as clinically indicated.	
CTCAE Grade for ALT and AST	Action
Grade 1 ($>ULN-3.0 \times ULN$), Grade 2 ($>3.0-5.0 \times ULN$), WITHOUT increase in total bilirubin above $2 \times ULN$	No dose modification required
Persistent or Recurrent Grade 2, or Grade 3 ($>5.0-20.0 \times ULN$), WITHOUT increase in total bilirubin above $2 \times ULN$	Suspend dose until toxicity resolves to baseline or Grade 1. Resume at next lower dose.
Elevation in AST and/or ALT $>3 \times ULN$ WITH total bilirubin $>2 \times ULN$, in the absence of cholestasis	Discontinue abemaciclib
Grade 4 ($>20.0 \times ULN$)	Discontinue abemaciclib

Details for hepatic monitoring depend upon the severity and persistence of observed laboratory test abnormalities. If a study patient experiences elevated ALT $5 \times ULN$ and elevated TBL $2 \times ULN$, or ALT $8 \times ULN$, liver tests, including ALT, AST, TBL, direct bilirubin, gamma-glutamyl transferase (GGT), and creatine phosphokinase (CPK), should be repeated within 3 to 5 days to confirm the abnormality and to determine if it is increasing or decreasing. If the abnormality persists or worsens, clinical and laboratory monitoring should be initiated by the investigator, based on the hepatic monitoring tests below in Appendix B.

Diarrhea

At enrollment, patients should receive instructions on the prompt management of diarrhea. In the event of diarrhea, supportive care measures should be initiated as early as possible. These include the following:

CONFIDENTIAL

This material is the property of the [UC Irvine Chao Family Comprehensive Cancer Center](#). Do not disclose or use except as authorized in writing by the study sponsor.

- At the first sign of loose stools, the patient should initiate antidiarrheal therapy (e.g. loperamide) and notify the investigator for further instructions and appropriate follow up.
- Patients should also be encouraged to drink fluids (e.g., 8 to 10 glasses of clear liquids per day).
- Site personnel should assess response within 24 hours.
- Refer to table below for additional information for diarrhea management and dose modification.

Diarrhea Dose Management Guidelines	
At the first sign of loose stools, start treatment with antidiarrheal agents, such as loperamide.	
CTCAE Grade	Action
Grade 1	No dose modification required
Grade 2	If toxicity does not resolve within 24 hours to ≤ Grade 1, suspend dose until resolution. No dose reduction is required.
Grade 2 that persists or recurs after resuming the same dose despite maximal supportive measures	Suspend dose until toxicity resolves to ≤Grade 1.
Grade 3 or 4 or requires hospitalization	Resume at next lower dose.

Dose level reductions should be made in 50 mg increments. For example, if the starting dose of abemaciclib for a study is 150 mg q12 hours, dose reduction 1 would be 100 mg q12 hours, dose reduction 2 would be 50 mg q12 hours.

General Guidance for Interstitial lung disease (ILD)/Pneumonitis events

Interstitial lung disease (ILD) / pneumonitis has been identified as an adverse drug reaction for abemaciclib. Adverse events reported included events such as interstitial lung disease, pneumonitis, obliterative bronchiolitis, organizing pneumonia, pulmonary fibrosis. The majority of events were Grade 1 or Grade 2 with serious cases and fatal events reported.

Monitor for clinical symptoms or radiological changes indicative of ILD/pneumonitis and please ask patients to report any new or worsening pulmonary symptoms. Symptoms may include hypoxia, cough, dyspnea, or interstitial infiltrates on radiologic exams.; these symptoms should be investigated and treated as per local clinical practice and/or guidelines (including corticosteroids as appropriate). Infectious, neoplastic, and other causes for such symptoms should be excluded by means of appropriate investigations. Investigations may include imaging such as high resolution computer tomography (HRCT), bronchoalveolar lavage (BAL), and biopsy as clinically indicated (see also Table).

Interstitial Lung Disease (ILD)/Pneumonitis

ILD/Pneumonitis Dose Management Guidelines	
CTCAE Grade	Action
Grade 1-2	No dose modification required
Grade 2 that persists or recurs after resuming the same dose despite maximal supportive measures within 7 days to baseline or Grade 1	Suspend dose until toxicity resolves to ≤Grade 1. Resume at next lower dose.
Grade 3-4	Discontinue abemaciclib

Non-hematological Toxicities (excluding Diarrhea, ALT Increased, and ILD Pneumonitis)

Non-Hematological Toxicity Dose Management Guidelines (excluding Diarrhea, ALT

CONFIDENTIAL

This material is the property of the [UC Irvine Chao Family Comprehensive Cancer Center](#). Do not disclose or use except as authorized in writing by the study sponsor.

Increased, and ILD Pneumonitis)	
Event	Action
Grade 1-2	No dose modification required
Persistent or recurrent Grade 2 toxicity that does not resolve with maximal supportive measures within 7 days to baseline or Grade 1	Suspend dose until toxicity resolves to baseline or ≤Grade 1. Resume at next lower dose.
Grade 3-4	

Note: Abemaciclib has been shown to increase serum creatinine due to inhibition of renal tubular transporters without affecting glomerular function (as measured by iohexol clearance). In clinical studies, increases in serum creatinine occurred within the first month of abemaciclib dosing, remained elevated but stable through the treatment period, were reversible upon treatment discontinuation, and were not accompanied by changes in markers of renal function, such as blood urea nitrogen (BUN), cystatin C, or calculated glomerular filtration rate based on cystatin C.

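### The Grade 2 ILD/pneumonitis suspend-and-reduce row is mis-drafted, so the protocol does not settle whether unresolved Grade 2 in a never-interrupted patient must be held and dose-reduced

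*Combined protocol and SAP*

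**What the plan says.** The ILD/Pneumonitis Dose Management Guidelines in section 4.2.1 have three rows.

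- For Grade 1-2 events the stated action is "No dose modification required".
- The second row, which is the one at issue, has as its trigger "Grade 2 that persists or recurs after resuming the same dose despite maximal supportive measures within 7 days to baseline or Grade 1". Its action is to stop dosing until the event is Grade 1 or better, then restart one dose level down.
- Grade 3-4: discontinue abemaciclib.

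The guidance above the table says of ILD/pneumonitis events that "The majority of events were Grade 1 or Grade 2 with serious cases and fatal events reported". For pulmonary symptoms it says that "these symptoms should be investigated and treated as per local clinical practice and/or guidelines (including corticosteroids as appropriate". It gives no instruction on holding the drug.

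The table for other toxicities is headed "Non-hematological Toxicities (excluding Diarrhea, ALT Increased, and ILD Pneumonitis", so it cannot be used to fill a gap in the ILD table.

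**The concern.** A dose-modification table should lead two treating physicians to the same action for the same patient. This row may not. Its trigger refers to a restart at an unchanged dose, and nothing in the ILD table produces one. Its seven-day clause has no verb, so the reader must infer that seven days is the time allowed for resolution.

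The protocol itself reports fatal ILD events and says that most events were Grade 1 or 2, the grades these two rows govern. What is at stake is narrow: whether suspension and dose reduction are compulsory or optional when Grade 2 pneumonitis does not resolve in a patient whose dosing was never interrupted.

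**Working it through.** The plan states no figure to reproduce. The check compares the wording of the tables and traces patients through them.

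**Where the trigger's parts also appear (section 4.2.1)**

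- *Diarrhea table.* Its first Grade 2 row says "If toxicity does not resolve within 24 hours to ≤ Grade 1, suspend dose until resolution. No dose reduction is required". That creates a hold with a restart at the same dose. The next row covers Grade 2 that persists or returns after such a restart. The ILD row opens with the same words but has no preceding row of this kind.
- *General non-hematological table.* Its row reads "Persistent or recurrent Grade 2 toxicity that does not resolve with maximal supportive measures within 7 days to baseline or Grade 1". The clause is complete and has no restart condition. The ILD row has the same ending without *that does not resolve*.
- *Hepatic table.* A general no-modification row is followed by a specific row for "Persistent or Recurrent Grade 2, or Grade 3", again with no restart condition.

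**Two readings of the ILD row**

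- Reading A: the restart condition governs both persistence and recurrence.
- Reading B: persistence stands alone. The specific row then overrides the general Grade 1-2 row, as in the hepatic and non-hematological tables.

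**Patients traced through each reading**

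| Patient with Grade 2 ILD | Reading A | Reading B |
|---|---|---|
| Never interrupted, not resolved at 7 days | No modification required | Suspend, restart one level down |
| Resolved on drug, then recurs without resolving | No modification required | Unclear: the restart condition sits beside recurrence, but the parallel tables treat persistent and recurrent alike |
| Doses interrupted, restarted at same dose, persists or recurs | Suspend and reduce | Suspend and reduce |

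The readings diverge only for patients who were never interrupted.

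**Dose difference (illustration only)**

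Inputs: start at 150 mg twice daily and reduce in 50 mg steps (4.2.1); holds of up to 14 days, longer if the principal investigator agrees (4.2.2).

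- Starting dose: 2 × 150 = 300 mg/day versus 2 × 100 = 200 mg/day after reduction.
- After one earlier reduction: 200 versus 2 × 50 = 100 mg/day.
- At 50 mg twice daily there is no lower level, and 4.2.1 says to discontinue if that dose is not tolerated.

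Assume a 28-day cycle, onset on day 1, event unresolved at day 7, and starting dose. Dose taken before any suspension is 7 × 300 = 2,100 mg.

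- No change at all: 28 × 300 = 8,400 mg.
- Reduced with no hold time: 2,100 + 21 × 200 = 6,300 mg (6,300/8,400 = 0.75, 25% less).
- 14-day hold, then reduced: 2,100 + 7 × 200 = 3,500 mg (3,500/8,400 = 0.417, 58% less).
- Hold to cycle end (21 days, needs the principal investigator's agreement): 2,100 mg (2,100/8,400 = 0.25, 75% less).

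**The case against.** The best defense is that the unsafe outcome needs the weaker reading and an investigator who then chooses not to act. A specific row normally overrides a general one, and the neighboring tables point the same way. A row saying that no modification is required does not forbid a hold.

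Other provisions also help. Section 4.2.2 permits holds and says that discontinuation should be considered when toxicity has not recovered within 14 days. Sections 4.5 and 5.6 (item 5.5.5) allow treatment to end for unacceptable or unsafe toxicity. The Appendix D pill diaries tell a patient with any symptoms to skip the dose and call. A patient who does so and restarts at the same dose has met the row's condition, so the protocol's own materials can supply the missing antecedent.

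All of this stands, and it shrinks the exposed group to patients without symptoms or those told to keep dosing. It does not close the gap. Sections 4.2.2, 4.5 and 5.6 leave the decision to judgment, and the diary sets no ILD dose change or restart dose. None of them makes suspension or a lower restart dose mandatory for unresolved Grade 2 ILD.

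A reader might infer more than the documents support:

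- That the protocol orders full dosing through unresolved pneumonitis. It does not; one reading merely fails to require a change.
- That the ILD table contains no hold at all. The disputed row itself orders a suspension. What is missing is a hold followed by a same-dose restart.
- That the milligram totals measure harm. No document links cumulative dose to ILD outcome.

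**Conclusion.** The drafting defect is certain from the text, and nothing suggests that a PDF break or redaction caused it. Its practical consequence is limited. Persistent Grade 2 is better read as requiring suspension and reduction, but the wording also permits leaving a never-interrupted patient with persistent or recurrent unresolved Grade 2 under the no-modification row.

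Work-up and treatment under local practice apply on either reading, and Grade 3-4 is unambiguous. The cycle totals rest on day-1 onset, the starting dose and, for the unchanged case, an investigator who neither holds nor reduces. They should carry no weight in judging severity. How many of the planned 30 or so patients would be affected cannot be estimated from the documents.

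The row should be corrected because it is an operative safety rule for a reaction with reported deaths. It has no bearing on the primary endpoint or the two-stage design.

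**What to change.** Reword the Grade 2 row so that either of two triggers leads to suspension until Grade 1 or better and restart at the next lower dose:

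1. the trigger already used in the general non-hematological table, "Persistent or recurrent Grade 2 toxicity that does not resolve with maximal supportive measures within 7 days to baseline or Grade 1"; or
2. Grade 2 that continues or returns following a hold and a restart at an unchanged dose.

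Limit the no-modification row to Grade 1 and to Grade 2 that does not meet the reworded row, so that the two cannot overlap. This restores the missing words, covers the never-interrupted patient and keeps the existing restart trigger.

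The cost is one table edit at the next amendment and a memo to treating staff.

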4.2.2 Dose Suspension and Cycle Delays

Both dose suspension (within a cycle) and cycle delay are permitted. Study treatment may be held up to 14 days within a cycle or at start of next cycle to permit sufficient time for recovery from the toxicity. Patients not recovering from toxicity within 14 days should be considered for discontinuation at the discretion of the investigator. In exceptional circumstances, a delay >14 days is permitted upon agreement with the principal investigator (PI).

A delay of a cycle due to holiday, weekend, bad weather, or other unforeseen circumstances will be permitted for a maximum of 7 days and not counted as a protocol deviation. In exceptional circumstances, a delay >7 days is permitted upon agreement with PI.

4.3 Fulvestrant Dose Modification and Management

4.3.1 Guidelines for Use in Patients with Hepatic Impairment:

A dose of 250mg is recommended for patients with moderate hepatic impairment (Child-Pugh class B). Faslodex has not been evaluated in patients with severe hepatic impairment (Child Pugh class C).

4.3.2 Guidelines for Use in Patients with Renal Impairment:

Negligible amounts of Fulvestrant are eliminated in the urine. No adjustment is recommended.

4.4 Concomitant Medications/Treatments

Any medication or vaccine (including over-the-counter or prescription medicines, vitamins, and/or herbal supplements) that the patient is receiving at the time of enrollment or receives during the study must be recorded along with:

- Reason for use
- Dates of administration including start and end dates

CONFIDENTIAL

This material is the property of the [UC Irvine Chao Family Comprehensive Cancer Center](#). Do not disclose or use except as authorized in writing by the study sponsor.

All treatments that the investigator considers necessary for a patient's welfare may be administered at the discretion of the investigator in keeping with the community standards of medical care.

All the concomitant medications and supportive therapy administered during the 30 days prior to the first dose until 30 days after the last dose must be recorded on the appropriate case report form (CRF).

Abemaciclib is predominantly cleared by oxidative metabolism via CYP3A4. Clinical drug interaction studies with a CYP3A inhibitor and CYP3A inducer significantly altered the PK of abemaciclib and its circulating major metabolites.

CYP3A Inducers

Avoid concomitant use of CYP3A inducers and consider alternative agents.

CYP3A Inhibitors

Avoid concomitant use of strong CYP3A inhibitors (for example, voriconazole) and use caution with coadministered moderate (for example, ciprofloxacin) or weak (for example, ranitidine) CYP3A inhibitors. If coadministration with a strong CYP3A inhibitor is unavoidable, reduce the abemaciclib dose to 100 mg twice daily or, in the case of ketoconazole, reduce the abemaciclib dose to 50 mg twice daily. In patients who have had a dose reduction to 100 mg twice daily due to adverse reactions, further reduce the abemaciclib dose to 50 mg twice daily. Avoid grapefruit or grapefruit juice. If a CYP3A inhibitor is discontinued, increase the abemaciclib dose (after 3-5 half-lives of the inhibitor) to the dose that was used before starting the inhibitor

General Guidance for use of Radiotherapy in Combination with Abemaciclib

Limited data are available with abemaciclib and radiotherapy or alternate dosing schedules (e.g. induction phase). Thus, caution should be exercised with administering abemaciclib with radiotherapy.

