The standard of care options for Post-menopausal patient who develop localized or locally advanced recurrent HR+ Breast cancer while on adjuvant endocrine therapy remains to be surgical resection. The treatment depends on the type of local treatment they received at the initial diagnosis. Recurrence can happen after a lumpectomy and radiation or following mastectomy. Mastectomy is the surgical standard of care for most patients with a local recurrence following breast conserving surgery and radiation. Surgery in the form of wide local excision is recommended for post mastectomy chest wall recurrence. The role of radiation in the management of localized recurrence also depends upon if patients received adjuvant radiation at the initial diagnosis. Surgery and radiation in recurrent HR + breast cancer only address local control. Patients with recurrent breast cancer are at risk of developing metastatic breast cancer, have microscopic metastasis and many have evidence of endocrine resistance. Furthermore, extensive loco-regional recurrence is not amenable to surgical resection alone. Surgery and radiation does not address endocrine resistance nor does it treat microscopic metastasis. Hence, addressing endocrine resistance as well as adopting a targeted Neo-Adjuvant approach based on patient's tumor profiling and then treating them with the Abemaciclib and Fulvestrant to downstage the tumor, limit chemotherapy induced toxicity is the next logical step in the management of patients. These patients often land up getting Neo-Adjuvant chemotherapy. Few achieve a complete pathologic response and many are subjected to severe peri-operative complications. Hence, there continues to be an unmet medical need to develop alternate therapies that are less toxic and provide better outcomes. Neoadjuvant endocrine therapy can be an alternative option to chemotherapy in Hormone Receptor positive (HR+) tumors, particularly for postmenopausal women. Unlike in premenopausal women, available data suggest that NET is associated with similar response rates and rates of breast- conserving surgery (BCS) as NACT with lower toxicity, although survival data with NET are not yet available (11-15).

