2.4 Endpoints

The primary endpoint is pathological complete response (pCR) as defined by no evidence of tumor cells in the final surgical specimen
The secondary endpoints are ORR per RECIST 1.1 criteria, recurrence disease-free and incidence of AEs

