- 3.1.11 Patients who received adjuvant radiotherapy must have completed and fully recovered from the acute effects of radiotherapy. A washout period of at least 14 days is required between end of radiotherapy and screening for the study.
- 3.1.12 Patients who received chemotherapy must have recovered (Common Terminology Criteria for Adverse Events [CTCAE] Grade ≤1) from the acute effects of chemotherapy except for residual alopecia or Grade 2 peripheral neuropathy prior to enrollment. A washout period of at least 21 days is required between last chemotherapy dose and enrollment (provided the patient did not receive radiotherapy).
- 3.1.13 Any known markers of response or resistance to CDK 4/6 inhibitors to be present in the biopsy specimen
- 3.1.14 If patients have been treated with prior Neo-Adjuvant chemotherapy at the time of primary diagnosis and not at the time of recurrence, they will be included in the study.
- 3.1.15 Must be able to sign a written informed consent, are reliable, willing to be available for the duration of the study and are willing to follow study procedures

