4.1.2 Supportive Care Guidelines

Necessary supportive measures for optimal medical care will be given throughout the study including antidiarrheal, blood components etc. Additional care will be administered as indicated by the treating physician and the subject's medical need. All the concomitant medications and supportive therapy administered during the 30 days prior to the first dose until 30 days after the last dose must be recorded in OnCore eCRF.

4.2 **Toxicities and Dosing Delays/Dose Modifications**

Any patient who receives treatment on this protocol will be evaluable for toxicity. Each patient will be assessed for the development of toxicity according to the Time and Events table (Section 5.4). Toxicity will be assessed according to the NCI Common Toxicity Criteria for Adverse Events (CTCAE), version 5.0. Dose adjustments should be made according to the system showing the greatest degree of toxicity.

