6.0 Measurement of Effect

6.1 Pathologic Complete Response (pCR)

No histologic evidence of microscopic invasive tumor at the primary tumor site in the surgical specimen (ypT0 or ypTis).

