10.0 STATISTICAL CONSIDERATIONS

Pathological response (pCR) is a tool to measure the efficacy of Neo-Adjuvant therapy. A complete pCR is defined as the absence of invasive cancer in the tumor and/or the axillary lymph node in the surgical pathology specimen after undergoing Neo-Adjuvant therapy. Chemotherapy can shrink HR- positive tumors and facilitate better surgical options, but is less likely to achieve a pathologic complete response (pCR) in HR-positive cancers, especially luminal A cancers, than for more proliferative histologies. Multiple metaanalysis have shown that pCR has prognostic implications even in patients with HR+ breast cancer. However, a limitation of using pCR to predict outcomes in patients with ER+ disease is that only 2 to 10 percent of patients with ER + disease achieve a pCR with NACT. In the post-menopausal setting, Aromatase Inhibitors are recommended over Tamoxifen as Neoadjuvant endocrine therapy based on clinical trials and meta-analysis. AIs resulted in higher clinical response rate (OR 1.69, 95% CI 1.36-2.10), radiologic response rate (OR 1.49, 95% CI 1.18-1.89), and BCS rate (OR 1.62, 95% CI 1.24-2.12) compared with tamoxifen (18).

Several trials have also investigated the role of endocrine therapy in combination with other targeted therapies. For example, in the randomized phase II UNICANCER-NEOPAL study, the combination of neoadjuvant palbociclib and letrozole resulted in slightly lower pCR rates compared with neoadjuvant third-generation chemotherapy, but the rates of clinical response and breast-conserving surgery were similar, with less frequent serious adverse events (19). Another study compared different doses of neoadjuvant fulvestrant (500 mg/month versus 250 mg/month) given for 16 weeks prior to surgery (20). Similar to what has been observed in the metastatic setting, the study demonstrated that the higher dose of fulvestrant was superior and had a greater antiproliferative effect. At week 16, tumor response rates were 22.9 and 20.6% for fulvestrant 500 and 250 mg, respectively, with considerable decline in all markers by both imaging and the ER/PR scoring method.

CONFIDENTIAL

This material is the property of the [UC Irvine Chao Family Comprehensive Cancer Center](#). Do not disclose or use except as authorized in writing by the study sponsor.

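### The plan has no rule for scoring pCR when non-protocol anticancer treatment is given before surgery, so such a pCR is not excluded from the Simon counts

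*Combined protocol and SAP*

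**What the plan says.** **Permission.** Section 4.4 states that "All treatments that the investigator considers necessary for a patient's welfare may be administered at the discretion of the investigator", within community standards of care. The specific restrictions that follow concern CYP3A inducers and inhibitors and grapefruit. On radiotherapy, the section notes that data are limited and concludes that "caution should be exercised with administering abemaciclib with radiotherapy". It does not address chemotherapy or other anticancer drugs.

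**Endpoint.** Section 2.4 gives the primary endpoint as "pathological complete response (pCR) as defined by no evidence of tumor cells in the final surgical specimen". Section 6.1 requires ypT0 or ypTis at the primary site. Section 10.0 defines pCR as absence of invasive cancer "in the surgical pathology specimen after undergoing Neo-Adjuvant therapy". These definitions differ in other respects, which is a separate matter. None makes the result conditional on which treatment was given. The objective in Section 2.1 asks about abemaciclib plus fulvestrant.

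**Entry.** Criterion 3.1.14 covers patients who had neoadjuvant chemotherapy "at the time of primary diagnosis and not at the time of recurrence, they will be included in the study". The distinction is made at entry, and no later section carries it forward.

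**Decision rule.** Section 10.2 stops the trial at 1 or fewer responses in 10, and otherwise rejects a 10% null at 6 or more in 29. Section 4.8 rules out replacement. Section 6.2.1 defines evaluability for toxicity, objective response and non-target disease, but not for pCR.

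**Recording.** Section 4.4 first requires any medication received during the study to be recorded, with dates and reason. Section 4.4 and Section 4.1.2 then set a window that runs "until 30 days after the last dose must be recorded in OnCore eCRF" (Section 4.4 names the case report form instead).

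**The concern.** The trial asks what abemaciclib plus fulvestrant achieves, but the endpoint records what the specimen shows after whatever was given. If a patient does poorly on study drug and receives chemotherapy or locoregional radiotherapy before surgery, a clear specimen satisfies all three definitions. No control arm would show the same contribution, so any such pCR moves the observed rate upward against a fixed 10%. The patients most likely to be given other treatment are those in whom the regimen has not worked.

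The decision boundaries are one patient wide: 1 versus 2 of 10, and 5 versus 6 of 29. With no scoring rule and no pCR-evaluable set, an analyst could count such a patient as a response, count the patient as a failure, or drop the patient. In an open-label trial that choice could be made with the result already known.

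**Working it through.** **Inputs from the documents.** n1 = 10, r1 = 1, N = 29, r = 5, p0 = 0.10, p1 = 0.30 (Section 10.2). pCR with neoadjuvant chemotherapy in ER+ disease is 2 to 10% (Section 10.0).

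**Reproducing the plan's design.**

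P(reject) = sum over x = 2 to 10 of Bin(x; 10, p) × P(Bin(19, p) ≥ 6 − x), the tail being 1 when x ≥ 6.

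- At p = 0.10: 0.0471 (plan: 0.0471).
- At p = 0.30: 0.8051 (plan: 0.8051).
- Early stopping at p = 0.10: 0.9^10 + 10 × 0.1 × 0.9^9 = 0.3487 + 0.3874 = 0.7361 (plan: 0.7361).
- Expected sample size: 10 + (1 − 0.7361) × 19 = 15.0 (plan: 15).

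**Adding other treatment.** Hold the true regimen pCR at the null 10%. Let f be the share of patients not cleared by the regimen who receive other anticancer treatment before surgery, and q the chance that it clears the tumor. The counted rate is

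p = 0.10 + 0.90 × f × q.

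For example, f = 20% and q = 10% give 0.10 + 0.90 × 0.20 × 0.10 = 0.118. The documents give no f, so 5-30% is an assumed range. q spans the plan's own 2-10%.

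| f | q = 2%: p, P(reject) | q = 5%: p, P(reject) | q = 10%: p, P(reject) |
|---|---|---|---|
| 5% | 0.1009, 0.0488 | 0.1023, 0.0515 | 0.1045, 0.0561 |
| 10% | 0.1018, 0.0506 | 0.1045, 0.0561 | 0.1090, 0.0662 |
| 20% | 0.1036, 0.0542 | 0.1090, 0.0662 | 0.1180, 0.0893 |
| 30% | 0.1054, 0.0581 | 0.1135, 0.0772 | 0.1270, 0.1163 |

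At q = 10%, the chance of stopping at stage 1 falls from 0.736 to 0.719 (f = 5%) and 0.631 (f = 30%).

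**In patients.** The expected number of extra pCRs in 29 is 29 × 0.90 × f × q. At f = 10% this is 0.05 (q = 2%) to 0.26 (q = 10%). At f = 30% and q = 10% it is 0.78.

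**If one extra pCR does occur.** With all other patients at 10%, one certain additional pCR raises the false-positive chance from 0.047 to 0.1285 if it falls in stage 1, or to 0.094 if it falls in stage 2.

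**Scoring such patients as non-pCR.** If a fraction f of all patients receives other treatment regardless of outcome, the counted rate is p × (1 − f).

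- f = 5%: rejection probability 0.0382 at p0 and 0.766 at p1.
- f = 10%: 0.0305 at p0 and 0.720 at p1.

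Type I error therefore stays at or below 0.0471, and power falls below the planned 80%.

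**The case against.** The intended pathway is study drug followed directly by surgery. The Study Summary and Section 1.4 describe it that way, and Section 2.1 ties pCR to the two study drugs. The phrase in Section 10.0 sits in a general definition of pCR, and the study regimen is the only neoadjuvant therapy the plan prescribes. The permission in Section 4.4 concerns patient welfare, and the radiotherapy paragraph is a warning. All of this shows intent. None of it says how to score a patient who departs from the pathway.

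Several stronger readings are tempting, and the documents do not support them:

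- **That the plan declares such a pCR a response, or that one makes the trial a success.** No sentence says it counts; it is simply not excluded. Success needs 6 of 29.
- **That the plan expects patients who fail study drug to receive chemotherapy.** The remark in Section 1.4, "These patients often land up getting Neo-Adjuvant chemotherapy", describes practice outside the trial and gives no basis for f. Section 4.5 lists reasons to stop treatment and does not mention surgery.
- **That later chemotherapy would go unrecorded.** The first recording sentence in Section 4.4 has no 30-day limit and covers any medication received during the study. The two sentences conflict, and neither plainly covers radiotherapy.
- **That the false-positive chance reaches 0.15 or more.** At f = 20%, values of 0.147 and 0.218 need q = 20% and q = 30%. The documents give no such rates, and no rate for radiotherapy. Section 1.4 reports no pCR in the three index patients given chemotherapy.

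The power cost of non-response scoring is also real, and reporting pCR regardless of other treatment is a defensible alternative if it is chosen in advance.

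**Conclusion.** The gap stands. Other anticancer treatment before surgery is not excluded, the endpoint depends on the specimen alone, and nothing says how the Simon counts treat a patient who receives it. The objective and the endpoint do not match on this point.

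At the plan's own chemotherapy pCR rates the inflation is negligible to moderate: 0.049-0.058 at q = 2% and 0.056-0.116 at q = 10%, against a nominal 0.0471. This rests on the assumed f of 5-30%; anything larger needs a q that the documents do not supply. It is a cheap improvement that should be made before results are seen, and it does not invalidate the design.

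**What to change.** In Sections 6.1 and 10.2, state that a patient who receives non-protocol anticancer treatment (chemotherapy, locoregional radiotherapy or other) between first study dose and surgery stays in the denominator and counts as non-pCR in the stage 1 and final counts. Report pCR regardless of such treatment as a supporting figure. Because the rule settles both numerator and denominator for these patients, they cannot be dropped afterwards.

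Reconcile the two recording sentences in Section 4.4, and the matching one in Section 4.1.2, so that all anticancer treatment, including radiotherapy, is recorded up to surgery.

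This takes a few sentences and one eCRF item. It is a scoring rule only and leaves patient care to the investigator. The price is a somewhat lower counted pCR rate and the loss of power shown above, which the sponsor should acknowledge when adopting the rule.
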